## 5.1.3.1 Postoperative Visit 1 - Operative Day (1 - 6 hours after surgery)

At approximately 1 - 6 hours after surgery, an IOP reading and slit lamp examination in the implanted eye(s) will be conducted. Any complications, AEs, or associated treatment given will be appropriately documented and reported in the CRFs.

## 5.1.4 Postoperative Visits Day 1 – 18

An IOP reading will be performed at these visits in addition to other standard postoperative assessments as part of the normal postoperative standard of care. Any AEs of increased IOP compared to baseline will be documented. Evaluation of the anterior chamber angle is to be performed by gonioscopy or AS-OCT in cases where gonioscopy is contraindicated as presented in Appendix B. Associated treatments will be appropriately documented and reported in the CRFs.

## 5.1.5 Unscheduled Visits

Additional visits may be scheduled, as necessary, to ensure the safety and well-being of subjects. All additional exams should be fully documented in the source documents and on Unscheduled Visit CRFs, as appropriate. Visits intended to fulfill scheduled visit requirements that fall outside the designated scheduled visit range, are not Unscheduled Visits. In these cases, the visit data will be collected and transcribed to the appropriate scheduled visit CRF.

#### 5.1.6 Missed Visits

If a subject misses any scheduled follow-up visit and cannot be seen prior to the start of the visit range for the next scheduled follow-up visit, the visit will be documented as missed in the source documents and CRFs.

## 5.2 Study Completion

STAAR Surgical will notify the Investigator when to contact the IRB to inform them that the study is complete.

## 5.2.1 Early Study Termination

If during the study it becomes evident to the Sponsor that the study should be stopped prematurely, the study will be terminated and appropriate notification will be given to the Investigator(s), IRB, and FDA, as applicable. STAAR Surgical will instruct the Investigators to stop dispensing study materials/treatment, to assure appropriate followup for all enrolled subjects and arrange for study closeout at each site as appropriate.

## 5.2.2 Post-study Follow-up

If a subject requires further follow-up of an Adverse Event/Serious Adverse Event (SAE) upon discontinuation or completion of the study, the Investigator should schedule poststudy follow-up visits, as necessary. Refer to **Section 6.3.4** for follow-up of SAEs following study exit.

## 5.3 Concomitant Medications/Therapy

The following medication regimen will be followed by all sites:

- topical 4th generation fluoroquinolone four times a day (QID) starting 3 days prior to surgery for a total of 10 days,
- topical non-steroidal anti-inflammatory drugs (NSAIDs) QID, twice a day (BID) or once a day (QD) per NSAID labeled dosing instructions for postoperative inflammation starting 3 days prior to surgery for a total of 10 days and then tapered weekly,

• topical steroid QID starting 3 days prior to surgery for a total of 10 days and then tapered weekly.

**Note:** No prophylactic systemic or topical IOP lowering medications (e.g., acetazolamide) will be used. Ocular hypotensive agents may not be used for prophylaxis of increased IOP because doing so will confound the results of the study.

During the study follow-up period, the Investigator may use any medical treatment that is judged appropriate and beneficial to the subject. All medications that are considered necessary for the subject's welfare may be used at the Investigator's discretion. Documentation of all medications and "other" non-medication therapy used for ocular indications by the subject during this study will be recorded in the subject's source document and applicable CRFs.

## 5.4 **Protocol Deviations**

The date of and reason for deviations will be documented in all cases. Significant or major protocol deviations impacting the safety of the subject, or the integrity of the study must be reported by the Investigator to the IRB immediately. Reporting of all other protocol deviations must adhere to the requirements of the governing IRB.

Protocol assessments will continue until the end of the study, unless the protocol deviations put the subject at risk or the subject's condition requires that he/she be discontinued from the study.

## 6.0 ADVERSE EVENT REPORTING

Throughout the course of this study, all efforts will be made to remain alert to possible AEs. If an AE occurs, the first concern will be the safety of the subject, and appropriate medical intervention will be made. All ocular AEs and all serious AEs (both ocular and non-ocular) and all interventions to treat these AEs (i.e., concomitant medications, release of aqueous from a pre-existing corneal incision or needle paracentesis, etc.) will be documented on source documents and reported to the Sponsor/designee in the CRFs. Non-serious non-ocular AEs will not be reported. The collection of AEs begins at the time the subject completes the informed consent process to participate in the study.

Refer to **Section 6.3.1** for instructions on events that require expedited reporting to the Sponsor.

## 6.1 Definitions

## 6.1.1 Adverse Event

An **Adverse Event** is any untoward medical occurrence in a subject that does not necessarily have a causal relationship to the study device and study protocol. Adverse events include **Adverse Device Effects** (ADEs, see **Section 6.1.2**).

Rev 2, 25Apr2023

## AEs Associated with IOLs

Adverse events associated with implantation of all types of Intraocular Lenses (IOLs) (i.e., aphakic and phakic), need to be reported as AEs on the AE CRF. These can include, but are not limited to the following:

- Complications during phakic IOL surgery
- Worsening of a pre-existing ocular condition during the study
- Chronic Anterior Uveitis: anterior chamber (AC) cells or flare of greater than grade 2 (using the Standardization of Uveitis Nomenclature, SUN criteria) at postoperative Visit 3 (Day 5 – 9) or later
- Clinically significant cystoid macular edema (CME): macular edema diagnosed by clinical examination and adjunct testing (e.g., optical coherence topography [OCT], fluorescein angiography) resulting in CDVA of 20/40 or worse at Visit 3 (Day 5-9) or later.
- Clinically significant corneal edema: corneal swelling (stromal or epithelial) at postoperative Visit 3 (Day 5 9) or later
- Endophthalmitis: intraocular inflammation requiring diagnostic vitreous tap and intraocular antibiotics,
- Mechanical pupillary block: shallowing of anterior chamber due to obstruction of aqueous humor flow from the posterior to anterior chamber through the pupil by the crystalline lens, vitreous face, or implanted device.
- Rhegmatogenous retinal detachment (RD): partial or complete RD associated with retinal tear.
- Toxic anterior segment syndrome (TASS): acute, non-infectious inflammation of the anterior segment that starts within 24 to 48 hours after surgery, usually resulting in hypopyon and commonly presenting with corneal edema and improving with steroid treatment.
- All Secondary Surgical Interventions (SSIs) and events that cause these interventions should be reported as AEs, regardless of when they occur.
  - For SSIs of secondary IOL intervention\*
    - Exchange investigational device is replaced with the same lens model
    - Removal investigational device is removed and replaced with a noninvestigational lens or no lens is implanted

Reposition – existing IOL is surgically moved to another location or rotated

\*Exchanges, removals, and repositions should be further subcategorized by the problem that caused the need for the intervention (e.g., pupil ovalization, subject-reported undesirable optical phenomena, damaged IOL, malpositioned IOL, lens optic abnormality, iris pigment epithelial loss, endothelial cell loss, incorrect IOL power, chronic anterior uveitis, cataract, etc.).

Experience with intraocular surgery and the implantation of IOLs has shown that some AEs can be considered normal or expected events after these procedures. Early, low grade anterior chamber cell/flare, corneal edema, and increase in IOP can often be considered normal or expected after phakic IOL surgery. They do not need to be reported as AEs if they occur prior to 1 week postoperatively AND if they meet the following criteria:

- AC cells or flare of grade 2 (using the SUN criteria) or less that require no change in standard postoperative medication regimen; if persisting to 1 week or more these should be reported as an AE.
- Corneal edema of ≤ grade 2 that does not reduce CDVA to 20/40 or worse and does not require any change in standard postoperative medication regimen; if corneal edema persists to 1 week or more it should be reported as an AE.
- Increased IOP that is <10 mmHg above baseline or is <25 mmHg and requires no change in standard postoperative medication regimen or any other special treatment. Any increased IOP ≥ 10 mmHg above baseline to a minimum of 25 mmHg or any increase in IOP that is treated in any way, should be reported as an AE regardless of whether it is observed before or after 1 week postoperatively.

- Loss of CDVA ≥10 letters up to 1 week postoperatively; loss of CDVA ≥10 letters at any time point > 1 week postoperatively should be reported as an AE.

All other untoward events that occur during the study, and all events that have sequelae should be reported as AEs, regardless of when they occur.

## AEs Associated with the ICL Platform

Ocular AEs associated with the ICL platform will be reported in this study. These can include, but are not limited to the following:

- anterior subcapsular opacities or clinically significant cataracts,
- narrowing of the anterior chamber angle,
- increased IOP,

- pupillary block,
- glaucoma,
- lens malposition,
- corneal endothelial cell loss (which may result in corneal edema),
- loss of CDVA,
- increase in refractive astigmatism,
- pigment dispersion,
- iris transillumination defects.

In addition, ocular AEs associated with the ICL platform may require a secondary surgery in the implanted eye(s). The following surgeries have been associated with the ICL platform:

- secondary IOL intervention (see above\*)
- vitreous aspiration
- iridotomy/iridectomy for pupillary block
- wound leak repair
- retinal detachment repair
- corneal transplantation

## 6.1.2 Adverse Device Effects

Adverse Device Effects are any untoward or unintended responses to a medical device. This definition may include any event resulting from insufficiencies or inadequacies in the instructions for use or the deployment of the device or other device malfunctions. This definition includes any event that is a result of a user error.

## **Device Deficiency**

A Device Deficiency is any inadequacy of the medical device with respect to its identity, quality, durability, reliability, safety or performance. This includes malfunctions, use errors and inadequate labeling. A malfunction is any failure of a medical device to perform in accordance with its intended purpose when used in accordance with the instructions for use or clinical study protocol. All device deficiencies are classified as product complaints and are to be reported to the Sponsor as described in **Section 6.3.3**.

## 6.2 Evaluation

Adverse events experienced in this study may be associated with the study device (i.e., ADE) or the study protocol.

When evaluating AEs, the Investigator must determine if the event is serious, assess the severity of symptoms, and evaluate the relationship of the event to the study device and study protocol, using the following guidelines:

A Serious Adverse Event is any AE (ocular or non-ocular) that:

- results in death
- results in serious injury, defined as:
  - life-threatening
  - permanent impairment of a body structure or function (e.g., blindness)
  - necessitates medical or surgical intervention to prevent permanent impairment to a body structure or a body function, or
  - results in a potentially sight-threatening condition
- is a malfunction that might cause or contribute to a serious injury or death if it were to recur
- requires in-patient hospitalization or prolongation of existing hospitalization
- leads to fetal distress, fetal death, a congenital abnormality, or birth defect

Hospitalization is a criterion for assessment of seriousness. Hospitalization in the absence of a medical AE is not in itself an AE. For example, the following reports of hospitalization without a medical AE should not be considered either serious, or an AE:

- administrative admission (e.g., for yearly monitoring exam)
- optional admission not associated with a worsening of a pre-existing condition (e.g., scheduled repair of the rotator cuff)
- hospitalization for admission without a medical AE

## Severity

- Mild: Subject awareness of a sign or symptom that is easily tolerated, requires no treatment, and does not interfere with the subject's daily activities
- **Moderate:** Subject awareness of a sign or symptom which may be a low level of concern to the subject and may interfere with daily activities, but can be relieved by simple therapeutic care
- Severe: A sign or symptom that interrupts the subject's daily activity and requires systemic therapy or other treatment

Relationship (Causality) to Study Device or Study Protocol

- Not Related: Adverse events which are clearly and incontrovertibly due to causes other than the study device or study protocol (e.g., concomitant disease, etc.)
- **Related:** Adverse events which are felt with a reasonable degree of certainty to be related to the study device or study protocol
- Unknown: Adverse events for which a connection with the study device or study protocol cannot be ruled-out with certainty, or not enough information is available to assess the relationship

All AEs, regardless of severity (Mild, Moderate or Severe) or causality (Not Related, Related, Unknown), will be reported to FDA.

## 6.3 Reporting

All untoward events (aside from the exceptions noted for the early postoperative period in **Section 6.1.1**) that occur during the study need to be reported as AEs.

All interventions used to treat AEs (i.e., concomitant medications, aqueous release from a pre-existing corneal incision or needle paracentesis to treat increased IOP) will be recorded in the subject's source document and applicable CRFs.

## 6.3.1 On-Site Expedited Reporting

The Investigator is obligated to report the following to the Sponsor within 24 hours of becoming aware of the event to ensure the safety of all participants in the study and to meet regulatory reporting requirements:

- all SAEs, regardless of relationship to study device or study protocol
- all **non-serious AEs** determined to be related to the study device (ADE)
- all device malfunctions that do not result in one of the above reportable events
- all secondary surgical interventions (removal, replacement or repositioning) involving the study lens

In addition, the following events are to be reported to the Sponsor as SAEs in this study:

- endophthalmitis
- pupillary block
- retinal detachment
- stromal thinning/corneal melting
- $\geq 2$  lines CDVA loss not secondary to any underlying condition

When reporting these events to the Sponsor, the site should forward any supporting documents along with the appropriate reporting form and the corresponding CRF, if applicable. Refer to the **Personnel and Facilities** section for Sponsor contact information for reporting of SAEs/ADEs and device malfunctions. Sites must also report applicable events to the reviewing IRB per its established reporting procedures.

**Note:** All device-related ADEs (SAEs or AEs related to the EVO ICL) must also be reported by the clinical site to STAAR Complaint Handling department according to STAAR Standard Operating Procedures (SOPs) for Complaint Handling.

## 6.3.2 Off-Site SAE Reporting

When participating in multicenter clinical trials, Principal Investigators may receive "offsite" reports (e.g., SAE Report). These are Sponsor reports of SAEs which occurred at other sites for the same trial, or in different trials using the same test article, that met the criteria for reporting to a regulatory agency. These should be reported to the reviewing IRB per their established reporting procedures. The IRB may require a revision to the ICF and reconsenting of patients if the SAE provides new information regarding risk to the study subject.

## 6.3.3 Reporting of Complaints for Ancillary Marketed STAAR Surgical Products

All information collected on a CRF could potentially be identified as a product complaint, as defined in **Sections 6.1.2** and **6.3.1**. During clinical monitoring by the Sponsor/designee, the information collected on the CRFs will be evaluated to determine if any of the information should be forwarded to the Sponsor for consideration as a complaint according to STAAR standard operating procedures for complaint handling. The Sponsor has the responsibility for evaluating and investigating potential complaints in accordance with STAAR's internal complaint handling procedures. Any complaints, malfunctions or similar events related to ancillary STAAR Surgical marketed products used in this study should be reported by the Investigators in accordance with the reference information provided on the commercial packaging.

## 6.3.4 Adverse Events and SAEs at Subject Exit

Ongoing ocular AEs at study exit will be documented as such in the CRFs and followed per the Investigator's standard of care.

Ongoing SAEs and ADEs will be followed until resolution or no further change in the condition is expected. Non-serious AEs that are ongoing at the study exit visit or upon discontinuation from the study will be followed per the Investigator's standard of care. Documentation in the eCRF of this follow-up is not required although subject care should continue as appropriate.

## 7.0 STATISTICAL METHODS

Analysis of the superiority of the proportion of primary eyes that have IOP  $\ge$  30 mmHg and IOP  $\ge$  40 mmHg at 1 – 6 hours postoperatively compared with the outcomes of Study CP19-01, i.e., 15.3% (50/327) primary eyes with IOP  $\ge$  30 mmHg, and 7.0% (23/327) primary eyes with IOP  $\ge$  40 mmHg (**Table 3**, below). Analysis of fellow eye rates will be used to support the findings of the two primary eye analyses.

Any deviations from the analysis plan will be documented in the final report.

Adverse Event - Elevated IOP	Primary Eyes (N=327)	All Treated Eyes (N=629)		
Number of elevated IOP events (n)	67	125		
Maximum IOP (mmHg)	n (%)	n (%)		
< 30	17 (5.2)	40 (6.4)		
≥ 30	50 (15.3)	85 (13.5)		
$\geq$ 40	23 (7.0)	38 (6.0)		
$\geq$ 50	13 (4.0)	24 (3.8)		
$\geq 60$	6 (1.8)	11 (1.7)		
$\geq 70$	0 (0.0)	1 (0.2)		

Table 3:	Maximum	IOP	Among	Incidences	of	Elevated	IOP	with	Onset	at
Postopera	tive Visit 0 (	Safety	y Populat	tion)						

Source: Table 13, EVO/EVO+ DFU

Percentage calculated as (n/N)\*100.

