## 7.1 Hypothesis

The observed rates of increased IOP seen in the absence of planned training in primary eyes in PMA Study CP19-01 were 15.3% (50/327) for IOP  $\geq$  30 mmHg and 7.0% (23/327) for IOP  $\geq$  40 mmHg. Based on Study CP19-01 data from investigators who followed the instructions in the proposed EVO Physician Certification Program regarding removal of OVD (Table 6), it is assumed that the proportion of primary eyes that will reach or exceed an IOP of 30 mmHg is 6% and the proportion of primary eyes that will reach or exceed an IOP of 40 mmHg is 1%.

Site #	Reported Irrigation Volume	with el IOP in s	ry Eyes levated specified ge (n)	Primary Eyes implanted	elevated specifie	es with I IOP in d range n)	All Implanted Eyes
	сс	>/= 30	>/= 40	Ν	>/= 30	>/= 40	Ν
09	10-20 cc	5	0	39	9	0	74
13	20-30 cc	3	0	19	7	0	37
07	10-20 cc	1	0	10	1	0	20
02	> 30 cc	1	0	11	2	0	20
10	10-20 cc	0	0	29	0	0	36
11	20-30 cc	1	0	76	1	0	148
04	> 30 cc	0	0	12	0	0	22
06	10-20 cc	0	0	8	0	0	12
03	10-20 cc	4	0	31	11	0	60
05	20-30 cc	0	0	5	0	0	9
	Total	15	0	240	31	0	438
Proportion, n/N		6.25%	0.00%		7.08%	0.00%	

Table 4: Incidence of elevated IOP in primary eyes for investigators who followed
proposed EVO Physician Certification Program instructions for removal of OVD. 

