## 7.2 Study Endpoints and Statistical Analysis

Primary endpoints of this study are:

- the proportion of primary eyes that have IOP ≥ 30 mmHg at 1 6 hours postoperatively
- the proportion of primary eyes that have  $IOP \ge 40 \text{ mmHg at } 1 6 \text{ hours}$  postoperatively

Secondary endpoints of this study are:

- the proportion of fellow eyes that have IOP ≥ 30 mmHg at 1 6 hours postoperatively
- the proportion of fellow eyes that have IOP ≥ 40 mmHg at 1 6 hours postoperatively

The following other endpoints of this study will be analyzed for the entire postoperative follow-up period (including the 1 - 6 hr postop Visit through Visit 4, postop Day 10 - 18):

- Rates of increased IOP in primary and all (primary + fellow) eyes attributed to retained OVD
- Rates of increased IOP in primary and all eyes attributed to other causes (e.g., pupillary block, steroid response, etc.)
- Rates of all categories of AEs (in primary and in all eyes)

The following will also be assessed in this study through postoperative Visit 4 using descriptive statistics:

- Device deficiencies,
- Distribution of lens vault measured by OCT,
- Slit lamp findings and distributions of gradings (e.g., anterior chamber cell and flare)
- Notable ophthalmoscopy findings;
- UDVA and CDVA
- Instances of loss of ≥10 letters of CDVA from baseline, along with analyses of the causes.

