## 7.3 Sample Size

For a single sample exact binomial test with a two-tailed alpha of 0.05 to demonstrate that a hypothesized rate of 6% is significantly lower than 15.3% for IOP spikes  $\geq$  30 mmHg with 98% power, a sample of 181 eyes would be required. Demonstrating that the rate of IOP spikes  $\geq$  40 mmHg is significantly lower, given a hypothesized rate of 1% vs the Study CP19-01 rate of 7%, a sample size of 181 primary eyes of 181 subjects will achieve 96% power. Power to achieve both endpoints can be conservatively estimated by

the product of the two powers, .98 times .96, or 94%. Analysis of fellow eye rates will also be conducted, and results will be used to support the findings of the two primary eye analyses. We assume no more than 10% loss to follow up in this 2-week study, so plan to enroll a minimum of 200 subjects (i.e., 200 primary eyes and 200 fellow eyes).

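### Do the secondary fellow-eye endpoints need a named reference rate, given that the two CP19-01 tables do not reconcile for fellow eyes?

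*Combined protocol and SAP*

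**What the plan says.** Section 7.2 lists two primary endpoints (primary eyes with IOP ≥30 and ≥40 mmHg at 1–6 hours). Under "Secondary endpoints of this study are" it then lists the same two proportions in fellow eyes. Section 7.0 sets the superiority comparison for primary eyes against 15.3% (50/327) and 7.0% (23/327) from Study CP19-01, and adds that "Analysis of fellow eye rates will be used to support the findings of the two primary eye analyses". Section 7.3 repeats that the fellow-eye "results will be used to support the findings of the two primary eye analyses".

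The test is a "single sample exact binomial test with a two-tailed alpha of 0.05", and 7.3 applies it to primary eyes: a "hypothesized rate of 6% is significantly lower than 15.3" per cent for ≥30 mmHg, and for ≥40 mmHg, "given a hypothesized rate of 1% vs the Study CP19-01 rate of 7" per cent. The Statistical Analysis part of 7.2 says discrete variables are summarised by frequencies and percentages. No section gives a fellow-eye comparator, hypothesis, test or success rule.

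CP19-01 counts appear in two tables. The IOP table in 7.0 (Table 3, Safety Population, sourced to the DFU) has 327 primary eyes and a column headed "All Treated Eyes (N=629". Table 4 in 7.1 covers ten sites that followed the OVD-removal instructions. It is sourced to a regulatory response, and has 240 primary eyes and 438 under "All Implanted Eyes". Section 7.1 cites it as Table 6.

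**The concern.** An endpoint that is meant to support a result needs something to be compared with. If the yardstick is left open, it can be picked once the data are in, and the only printed one is lenient for fellow eyes. CP19-01 fellow eyes did better than primary eyes (11.6% against 15.3% at ≥30 mmHg). Judging the new fellow eyes against 15.3% could therefore credit the certification programme with a first-eye to second-eye difference that existed before it.

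The obvious remedy is to derive a fellow-eye rate from the tables, and that meets a second difficulty. The fellow-eye counts in the two tables cannot both be right if the tables describe the same eyes. That raises the question whether any CP19-01 count in Section 7, including those behind the primary null values, can be trusted.

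**Working it through.** **1. The plan's own figures.** Inputs from 7.3: n = 181, two-sided 0.05 (lower tail ≤0.025), null rates 15.3% and 7%, assumed rates 6% and 1%. The test rejects when X ≤ c, where c is the largest count with P(X ≤ c | p0) ≤ 0.025. Power is P(X ≤ c | p1).

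- ≥30 mmHg: c = 18 (tail 0.0242), power 98.7%; stated 98%.
- ≥40 mmHg: c = 5 (tail 0.0111), power 99.0%; stated 96%.
- With each cut-off one event lower (17 and 4), power is 97.5% and 96.4%, product 94.0%. This matches all three stated figures.

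The stated power is met or slightly conservative, and no fellow-eye count enters it.

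**2. Fellow-eye rates by subtraction.**

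| | Fellow eyes | ≥30 mmHg | ≥40 mmHg |
|---|---|---|---|
| Table 3 (7.0) | 629 − 327 = 302 | 85 − 50 = 35 (11.6%) | 38 − 23 = 15 (5.0%) |
| Table 4 (7.1) | 438 − 240 = 198 | 31 − 15 = 16 (8.1%) | 0 |

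Exact 95% intervals for the Table 3 rates are 8.2–15.7% and 2.8–8.1%. Table 3 is coherent within itself (17 + 50 = 67, 40 + 85 = 125, percentages check), so a historical fellow-eye rate can be had from that table alone.

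**3. Reconciling the tables.** Subjects outside the ten sites: 327 − 240 = 87. Fellow eyes outside them: 302 − 198 = 104. With one fellow eye per subject at most 87 are possible, so 104 − 87 = 17 are in excess. Table 4's columns add up as printed (15, 240, 31, 438), so its total is not a misprint. Two rows have few fellow eyes: site 10 (36 − 29 = 7 for 29 subjects, 24%) and site 06 (12 − 8 = 4 for 8, 50%). The other sites run from 80% to 100%. Which count is off, or whether the two populations differ, cannot be settled from the documents.

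**4. Where the disputed numbers are used.** The null rates are 50/327 and 23/327, from the primary column of Table 3. The 6% rests on 15/240 = 6.25%, from the primary columns of Table 4; the matching count for ≥40 mmHg is 0/240, and the plan assumes 1%. The all-eyes totals, 629 and 438, enter none of these.

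**5. How much the reference would matter if a test were added.** Assume 181 fellow eyes and the primary-eye test.

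| Threshold | Reference | Cut-off | Power, plan's assumed rate | Power, 16/198 |
|---|---|---|---|---|
| ≥30 | 15.3% | 18 | 98.7% (at 6%) | 85% |
| ≥30 | 11.6% | 12 | 71% (at 6%) | 29% |
| ≥40 | 7.0% | 5 | 99% (at 1%) | – |
| ≥40 | 5.0% | 3 | 89% (at 1%) | – |

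For ≥30 mmHg the two references disagree when X is 13 to 18. That probability is 0.987 − 0.708 = 28% at a true 6%, and 0.854 − 0.290 = 56% at 8.1%. For ≥40 mmHg it is 0.990 − 0.891 = 10% at 1%. The 8.1% comes from the Table 4 all-eyes column that step 3 puts in doubt.

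**6. Is there a first-eye to second-eye difference?** In Table 3, 50/327 against 35/302 gives Fisher p = 0.20 (unpaired, since pairing is not available). In Table 4 the direction reverses: 6.25% primary, 8.1% fellow. The tables do not establish such a difference.

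**The case for a change.** The strongest case for a change is that these are the only named secondary endpoints and that a rate which can be derived is not a rate that was specified in advance. Table 4's fellow-eye rate predicts 0.0808 × 181 = 14.6 events, inside the 13–18 band where the two references disagree. On that rate the likeliest outcome is one where a claim of support turns on an unstated choice. A sentence in 7.2 and one check of the counts would settle it, with no added subjects.

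Part of this stands. The plan is silent on the comparator, the subtraction is right, and a report that set fellow eyes only against 15.3% could flatter the result. But the band matters only under a formal fellow-eye test, which the plan does not propose. A tabulated proportion does not flip: a reader can set it beside both the primary-eye and the fellow-eye CP19-01 rates, since the IOP table in 7.0 yields both. The prediction of 14.6 events also depends on Table 4's questioned total. At the plan's own 6%, the expected count is 0.06 × 181 = 10.9, below both cut-offs.

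**Conclusion.** No change follows. The missing comparator is a detail that an analyst fills sensibly: report the fellow-eye proportions descriptively, with the CP19-01 fellow-eye rates (11.6% and 5.0%) available for context. The study's conclusion rests on the two primary-eye tests, whose null rates, cut-offs (18 and 5 of 181) and power do not use any fellow-eye count.

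The excess of at least 17 fellow eyes is a discrepancy in background data. It assumes one primary eye per subject in CP19-01 and the same population and data cut in both tables. The sources and labels differ (treated eyes in a safety population against implanted eyes), so neither assumption can be confirmed here. Resolving it would alter no planned result. The citation of Table 6 in 7.1 is a clerical slip, since the table concerned is printed there as Table 4.

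The view would differ if a formal fellow-eye test or success claim were introduced. The choice of reference would then matter for ≥30 mmHg (28% to 56% chance of a different answer with 181 fellow eyes, at true rates of 6% and 8.1%) and much less for ≥40 mmHg (10% at a true 1%).
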